1.0 Research Introduction

1.1 Purpose/Specific Aims

This pilot study (R21), which is being funded by the National Center for Complementary and Integrative Health (NCCIH), aims to evaluate the impact of a novel intervention, Mindfulness Oriented Recovery Enhancement (MORE), on opioid use and chronic pain among individuals receiving methadone maintenance treatment (MMT). The main goal of this pilot study is to test the feasibility of our study methods before conducting a clinical trial to assess MORE with respect to a range of clinical outcomes. This study will involve a 2-arm individually randomized controlled trial design that compares MORE and treatment as usual (TAU).

A. Objectives

The main objective of this pilot study is to establish study feasibility in recruiting, retaining, and following up with MMT patients in the MORE and TAU interventions. Will track the following:

- When approached by study staff, the number of individuals who express interest in the study and the number who refuse (and reasons for refusal).
- The number of individuals who contact the staff with interest in the study.
- The number of individuals screened and eligible/ineligible.
- The number of individuals consented.
- The number of individuals who refuse participation after/during consent process.
- The number of sessions completed by study participants.
- The number of participants who drop out and reasons for drop out.
- Reasons for missed sessions.
- Tracking of all contact with participants for scheduling follow-up assessment sessions and completed/missed assessments.

In addition, the study will explore outcomes among participants in the MORE condition relative to treatment as usual (TAU) in regard to opioid use outcomes such as:

- Time until first opioid lapse
- Time until MMT dropout
- Total days of methadone treatment
- Total days of opioid or any drug use
- Trajectories of positive and negative affect
- Drug craving
- Pain severity and pain interference

B. Hypotheses / Research Question(s)

This is a pilot study designed to determine study feasibility and evaluate the impact of a novel intervention, MORE, on opioid use and chronic pain among individuals receiving methadone maintenance treatment. We will evaluate progression to a larger study based on the success of three key milestones. For the pilot study, we plan to evaluate our ability to recruit participants into the study, defining successful recruitment as 75% or more of our planned sample size by month 7. Retention will be considered successful if 50% of participants attend at least 4 MORE sessions, and will be assessed at month 9. We will evaluate our ability to collect 8-week and 16-week follow up data, defining success as a follow-up rate of 65% of participants at 8-weeks and 50% of participants at 16-weeks assessed at month 11. In addition to evaluating study feasibility through obtaining these milestones, we will obtain information about the efficacy of MORE on opioid use and chronic pain among MMT patients. It is hypothesized that: 1) Participants in MORE will have a longer duration of time to first opioid lapse than TAU participants; 2) Participants in MORE will have a longer duration of time to MMT dropout than TAU

participants; 3) At 8 and 16 –weeks post-enrollment, the MORE group will have fewer days of opioid use and fewer days of any drug use; 4) At 8 and 16 –weeks post-enrollment, the MORE group will have more days of methadone treatment than the TAU group; and 5) At 8 and 16 –weeks post-enrollment, the MORE group will have greater decreases in pain severity and pain interference than the TAU group.

1.2 Research Significance (*Briefly describe the following in 500 words or less*):

Despite the proven effectiveness of medication-assisted treatment (MAT) on opioid-use disorder (OUD), approximately 50% of people who begin methadone maintenance treatment (MMT) discontinue within twelve months, and 50% of people retained in MMT have an opioid relapse within six months.^{1,2} Research also suggests that pain, which is highly prevalent in MMT patients (with 55%-61% of patients reporting current chronic pain and 80%-88% experiencing pain in the last week), may be an important contributor to MAT dropout, opioid relapse, and opioid overdose.³ Unfortunately, effective pain management in MMT patients is challenging, as practitioners are reluctant to prescribe opioid pain medications to those with a history of substance use disorder.⁴ Therefore, alternative interventions are critical to help people in treatment for OUD to cope with their pain and improve their quality of life.

Mindfulness Oriented Recovery Enhancement (MORE) is a novel intervention that addresses drug use and chronic pain, and is unique among current OUD interventions in that it helps break negative reinforcement cycles by modifying the associative learning mechanisms that process drug and non-drug related cues.^{5,6} As a result, MORE promotes biobehavioral changes that strengthen responses to natural rewards while reducing responses to drug rewards, making the intervention more effective in helping people in MMT manage their pain and maintain long-term drug abstinence.^{5,6} MORE, which integrates training in mindfulness, cognitive reappraisal skills, savoring of natural rewards and positive emotion regulation into an 8-week group therapy, is designed to target the attentional biases, affective dysregulation, and autonomic stress responses that underlie the feedback loop between chronic pain, craving, and opioid misuse^{6,7} While MORE has shown positive outcomes in pain patients misusing, or at risk of misusing, opioids, it has not yet been tested in OUD patients with pain who are in recovery or receiving MAT. Therefore, we propose to test this promising intervention among individuals with pain who are receiving MMT for an OUD.

This study is significant because it could provide an additional and, as compared to existing behavioral interventions, a potentially more effective option for preventing relapse and managing chronic pain in people receiving MAT. Specifically, if found to be effective, MORE could help people on MAT cope with the stress and dysfunction associated with pain, reduce their risk of relapse, and enhance their overall quality of life.

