1.3 Research Design and Methods

This pilot study is a 2-arm individually randomized controlled trial design in which outcomes of MMT patients randomized to MORE are compared to outcomes of those randomized to treatment as usual (TAU). In the pilot study (R21; N=31), we will randomize MMT patients with chronic pain to MORE (n=15) or TAU (n=16). This study phase will focus on establishing study feasibility in recruiting, retaining, and following up study participants before progressing to a larger Phase II clinical trial (R33, N=150). Participants with pain who are receiving MMT for an opioid use disorder (OUD) will be recruited from the New Brunswick Counseling Center (NBCC) and the Lennard Clinic.

A. *Describe, in order of occurrence, all research procedures being performed, when and where they are performed, and by whom (including procedures being performed to monitor subjects for safety or minimize risks).*

Participants will be recruited through flyers posted in the clinics, being approached by research assistants in the waiting room of their usual methadone clinic (New Brunswick Counseling Center or Lennard Clinic), and referral by clinic staff. The number of individuals who contact the study staff through the flyers or referral and who are approached by study staff in the clinics will be tracked. Number of individuals who refuse study participation and who consent to the study will also be tracked. If an individual is interested in study participation, a trained research assistant will lead the individual through the informed consent process in a private space.

Participants randomized to the MORE condition will participate in eight, weekly, two-hour group sessions led by a clinic or study counselor. Each session will contain 4-8 participants and take place in a private room at the New Brunswick Counseling Center (NBCC) or the Lennard Clinic. Attendance at each session and reasons for missing sessions will be recorded. Participants randomized to the control condition will continue receiving treatment as usual at the NBCC.

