All study participants will participate in three face-to-face assessments at baseline, 8-weeks, and 16-weeks. If participants are unable or unwilling to attend a research appointment at their clinic, a research assistant will conduct a telephone interview. Information will be collected on demographic characteristics, substance use, methadone treatment, opioid craving and withdrawal, physical pain, non-reactivity, negative and positive affect, attentional bias, cognitive and mental health, physical health, and intervention implementation and attitudes. At the baseline and 8-week research visits, participants will complete three cognitive tasks on a computer that assess inhibitory control, implicit (automatic) associations, and the precedence of global features in visual perception. Urine and/or saliva samples will be requested at each assessment for confirmation of self-reported drug use. In addition, participants will partake in daily ecological momentary assessments (EMA) throughout the 16-weeks of study participation that include brief measures of pain intensity, mood, and substance use. Additionally, participants will be asked to initiate communication via smartphone when they either lapse to opioid use or experience serious craving. Self-initiated responses will include information about the circumstances surrounding their craving/lapse. A synopsis of all study instruments are included below (see 1.9B – Study instruments).

C. Define the duration of the study and the length of time each subject will participate in the study.

This pilot study is expected to take one year. Each subject will participate in the study for a total of 16-weeks.

Describe any primary and secondary study or safety endpoints

Feasibility will be assessed according to recruitment, retention and follow-up benchmarks. We will consider recruitment and retention efforts successful if we are able to enroll 75% of our target enrollment (31 participants) within a period of 4 months. Although we expect to recruit 100% of our planned sample by month 7, we set the criterion at 75% because we could adapt strategies for the next study to increase recruitment (including adding more MMT sites), if necessary. Retention will be considered successful if 50% of participants attend at least 4

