MORE sessions. We will consider our ability to follow participants successful if we obtain 8-week assessments from at least 65% of participants and 16-week assessments from at least 50%. Although we are targeting a follow-up rate in both groups of at least 80% and 75% at 8 and 16 weeks, respectively, we set the benchmarks at 65% and 50% because, again, if necessary, we can adapt follow-up strategies for the next study, based on lessons learned in this study.

Preliminary outcome measures to be assessed during this pilot study will be time until opioid lapse and MMT dropout. Preliminary secondary outcomes will be: days of methadone medication use, days of opioid and other drug use, and changes in pain severity and intensity. Additional measures are described below.

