1.4 Preliminary Data

Effects of MORE on cognitive, affective, and psychophysiological mechanisms implicated in addiction.

[name] conducted the first pilot randomized controlled trial (RCT; N=53) of MORE, and found that, relative to a support group (SG) control, MORE significantly decreased stress, modified addiction attentional bias, and increased heart rate variability recovery from substance cues during an affect-modulated cue-reactivity protocol. Two follow-up studies (N=58) found that trait mindfulness among substance dependent individuals in treatment was negatively associated with addiction attentional bias and positively associated with heart rate variability recovery from stress-primed cue-exposure.^{8,9}

MORE as a treatment for opioid misuse and chronic pain – preliminary outcomes and processes.

[name] recently completed a pilot RCT of 8 sessions of MORE for chronic pain patients receiving long-term opioid analgesic therapy.⁷ In the course of 1.5 years, 304 patients were recruited from community sources, 115 of whom met study criteria and were randomly assigned to treatment. Eighty-one percent of participants who began the study treatments completed treatment and were retained at the post-treatment assessment. Intent-to-treat analyses indicate that compared with a support group (SG; n=58) control, MORE (n=57) led to significant reductions in pain severity ($p=.014$, $d=.63$) and functional interference ($p=.002$; $d=.84$) that were maintained at 3-month follow-up and mediated by non-reactivity and reinterpretation of pain as innocuous sensory signals. Importantly, MORE improved addiction-related outcomes. Relative to SG, a greater proportion of opioid misusers treated with MORE no longer exceeded the validated threshold for opioid misuse following treatment, due to reductions in aberrant drug-related behavior, $\chi^2=3.74$, $p=.05$. MORE also significantly reduced opioid craving by post-treatment ($p=.027$, $d=.50$), and significantly decreased the correlation strength between craving and misuse.⁷

MORE and ecological momentary assessment of pain and affect.

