4.0 Research Data Source/s

4.1 Primary Data-Subjects and Specimens

4.2 Subject Selection and Enrollment Considerations

A. Recruitment Details

Thirty participants will be recruited from the New Brunswick Counseling Center (NBCC) or the Lennard Clinic. Participants will be recruited from flyers providing study information posted in the methadone clinic. In addition, clinic staff will refer potential participants to the study and research assistants will recruit on-site at the clinic. The research assistant will approach clinic clients in the waiting area at different times and on different days of the week to ensure adequate sampling. The research assistant will introduce him/herself to individuals waiting in clinic waiting areas, tell them they are conducting a study of an intervention for people with chronic pain and in methadone treatment, and ask them if they are interested in hearing more about the study. Patients expressing initial interest in the research will be given more detailed study information by the RA and screened for study eligibility.

B. Source of Subjects

Participants will be recruited from the New Brunswick Counseling Center (NBCC) and the Lennard Clinic.

C. Method to Identify Potential Subjects

Research assistants will screen individuals for eligibility after identifying interested individuals receiving services at NBCC or the Lennard Clinic.

D. Subject Screening

▪ Inclusion Criteria

Subjects must be age 18 or older, English-speaking, been in methadone treatment for at least 3 months, and experience a non-malignant pain with an intensity level of 8 or higher on the Gracely Box Scale¹³ for a duration of 2 months or longer.

▪ Exclusion Criteria

Subjects will be excluded from participation if they do not meet the inclusion criteria above exhibit cognitive impairment (score <24 on the Mini Mental Status Exam¹⁹) or psychosis (positive SCID Psychotic Screen²⁰), are at suicidal risk (positive score on ASQ Suicide Risk Screening Tool²³), or unable to attend group sessions due to distance, work, commitments or other logistical problems, or are currently pregnant or breastfeeding or planning to be pregnant or breastfeeding the next 16 weeks.

E. Recruitment Materials

Flyers with study information and a phone number to reach research staff will be posted throughout the New Brunswick Counseling Center (NBCC) and the Lennard Clinic.

F. Lead Site Recruitment Methods

N/A

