4.3 Subject Randomization

Since MORE is a closed group, we will randomize cohorts of 10-16 participants (depending on speed of recruitment) at each site to TAU or MORE with block randomization. Once we recruit at least 10 participants at a particular clinic, we will randomize participants to MORE or TAU, and the MORE group will begin. We estimate that we will recruit at least 10 participants per month.

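### Does the retention milestone, set as 50% of participants attending at least 4 MORE sessions, need its denominator rewritten?

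*Combined protocol and SAP*

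**What the plan says.** Section 1.1 B sets out how the team will decide on the larger trial: "We will evaluate progression to a larger study based on the success of three key milestones". The retention milestone is "Retention will be considered successful if 50% of participants attend at least 4 MORE sessions", to be assessed at month 9. The endpoints text in section 1.3 repeats it: "Retention will be considered successful if 50% of participants attend at least 4" MORE sessions. Neither place names an arm, and the analysis plan in section 6.1 A does not supply one.

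The planned arm sizes are in section 1.3: "we will randomize MMT patients with chronic pain to MORE (n=15) or TAU (n=16". The same section gives the eight weekly MORE sessions to those randomised to MORE, while controls continue usual treatment. Section 1.9 B logs the number of sessions completed and, at week 8, records sessions completed and missed for each participant.

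The neighbouring follow-up milestone is also expressed over participants: "8-week assessments from at least 65% of participants and 16-week assessments from at least 50" per cent. The text then separately mentions higher targets of 80% and 75% in both groups.

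**The concern.** Feasibility is the main objective of this pilot, and progression to a trial of 150 is evaluated on these milestones, so a threshold with an open denominator deserves a look. There are three worries.

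- Read literally over everyone randomised, the criterion cannot be met at the planned split.
- If the MORE arm is meant, the text does not say whether people who never start count. The preliminary data in section 1.4 report an earlier trial's retention among starters: "Eighty-one percent of participants who began the study treatments completed treatment and were retained at the post-treatment assessment". If the choice were left to month 9, it could be made with attendance already known.
- The follow-up benchmarks name no arm, so good follow-up under usual treatment could mask loss in the MORE arm.

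**Working it through.** **Inputs.** MORE 15, usual treatment 16, total 31 (section 1.3); retention threshold 50% (section 1.1 B). The protocol gives no required count to reproduce; its arm sizes do add up (15 + 16 = 31). The count needed is 50% of the denominator, rounded up.

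**All randomised.** 0.5 × 31 = 15.5, so 16 are needed. At most 15 can attend, and 15/31 = 48.4%. With the thirty participants of section 4.2 ("Thirty participants will be recruited from the New Brunswick Counseling Center (NBCC) or the Lennard Clinic") split 15/15, all 15 would have to attend at least 4 sessions. At a true attendance rate of 90% that has probability 0.9^15 = 0.21. Section 4.3 randomises in blocks by cohort and site ("we will randomize cohorts of 10-16 participants (depending on speed of recruitment) at each site to TAU or MORE with block randomization"), so the final split may not be exactly 15/16, but near-equal splits behave the same way. No team would set itself such a rule, so this reading can be set aside.

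**Randomised to MORE.** 0.5 × 15 = 7.5, so 8 are needed (53.3%); 7 of 15 is 46.7% and fails. P(Bin(15, p) ≥ 8) is 0.21, 0.50, 0.79 and 0.95 at p = 0.4, 0.5, 0.6 and 0.7. This is a workable criterion for a pilot.

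**Began MORE.** With 10 to 14 starters (an assumption), 5 to 7 attendees would suffice. The verdict can differ: if 3 of 15 never start and 6 attend at least 4 sessions, 6/12 = 50% passes and 6/15 = 40% fails. To see how often this matters, let s be the chance of starting and q the chance that a starter attends at least 4 sessions. The documents give neither.

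- Over those randomised: P(Bin(15, sq) ≥ 8).
- Over those who began: the sum over k of P(Bin(15, s) = k) × P(Bin(k, q) ≥ k/2 rounded up).

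| s | q | Pass, randomised | Pass, began |
|---|---|---|---|
| 0.70 | 0.60 | 0.26 | 0.79 |
| 0.80 | 0.60 | 0.44 | 0.80 |
| 0.90 | 0.60 | 0.62 | 0.81 |
| 0.95 | 0.70 | 0.91 | 0.96 |
| 0.90 | 0.80 | 0.97 | 0.995 |

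The gap is large only if many never start and attendance among starters is modest. Two design features work against never starting: section 4.2 excludes people who cannot attend group sessions, and section 4.3 randomises only once at least 10 people are recruited at a clinic, after which the group begins.

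**Which reading the text supports.** Section 1.3 A calls people participants from randomisation onward. The week-8 count in section 1.9 B covers each participant, so a never-starter is recorded with no sessions. The starter phrase in section 1.4 describes a result from an earlier trial in another population, and the same paragraph reports intent-to-treat analyses. Nothing limits this trial's milestone to starters.

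**Follow-up.** Pooled, 0.65 × 31 = 20.15 gives 21, and 0.5 × 31 = 15.5 gives 16. At 16 weeks, 12/16 under usual treatment plus 4/15 in MORE (27%) would pass. With 75% follow-up under usual treatment and an assumed 40% in MORE, the pooled rule passes with probability 0.84 and a per-arm rule with 0.21. But the benchmarks read plainly as pooled, the both-groups figures are targets that section 1.3 distinguishes from the benchmarks, and the documents give no basis for so wide a gap between arms.

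**The case for a change.** The strongest case for a change is that the literal rule is unattainable, that inferring the MORE arm does not by itself settle randomised versus began, and that one added sentence would cost nothing and would close off a choice made after attendance is known. The gap in the wording is real, both statements of the milestone share it, and the worked example does reverse the verdict.

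Less of this survives than first appears. The unattainable reading shows loose wording rather than a likely wrong decision, because nobody would score usual-treatment participants on sessions they are not offered. The choice between randomised and began rests on one phrase about another study and on assumed start rates. The milestone is also not an automatic gate: section 1.10 has the team summarise feasibility for the funder and seek approval to continue. With sessions completed, dropouts and reasons for missed sessions all logged, that report can show the number randomised to MORE, the number who began and the number attending at least 4 sessions. A favourable choice of denominator would then be visible. Arm-level loss to follow-up can likewise be seen in the dropout comparison (section 6.1 A) and is open to the monitoring board's review of retention and follow-up (section 6.3).

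**Conclusion.** No change to the plan is called for. The milestone leaves its denominator unwritten, but the design supplies it: at least 50% of those randomised to MORE, with never-starters counted as not retained. That is 8 of 15 if 15 are randomised to MORE, or half of whatever number is, rounded up. The all-31 reading (16 needed, 15 possible) rules itself out. The began reading would matter only with an appreciable number of never-starters: at an assumed 80% starting and 60% of starters attending, the pass probability is 0.44 against 0.80; at 95% and 70% it is 0.91 against 0.96. The follow-up benchmarks are pooled as written, and the plan already provides for looking at loss by arm. This conclusion assumes that analysts score attendance as randomised, as the session records allow. Writing the denominator down would be tidy, but it would change no sample size, procedure or analysis and, on the natural reading, no result.

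### Should the 65% and 50% follow-up benchmarks for progression be required in each arm rather than overall?

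*Combined protocol and SAP*

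**What the plan says.** Section 1.1 B states "We will evaluate progression to a larger study based on the success of three key milestones". The milestones are recruitment ("defining successful recruitment as 75% or more of our planned sample size by month 7"), retention ("Retention will be considered successful if 50% of participants attend at least 4 MORE sessions") and follow-up ("defining success as a follow-up rate of 65% of participants at 8-weeks and 50% of participants at 16-weeks assessed at month 11"). The endpoints text in section 1.3 C repeats the last one: follow-up succeeds "if we obtain 8-week assessments from at least 65% of participants and 16-week assessments from at least 50" per cent. Both places count participants, and neither names an arm.

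The next sentence of section 1.3 C gives higher targets, 80% at 8 weeks and 75% at 16 weeks, and says these are for both groups. It then explains that the benchmarks are set lower because follow-up methods can be adapted for the next study. The both-groups qualifier is not repeated for the benchmarks.

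Sections 1.3 and 1.5 give 15 in MORE and 16 in TAU, and section 4.5 A gives a total of 31.

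**The concern.** Section 1.1 A gives the main objective as to "establish study feasibility in recruiting, retaining, and following up with MMT patients in the MORE and TAU interventions". A pooled percentage does not test that arm by arm: good follow-up in one arm can carry poor follow-up in the other.

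There is a reason to expect a difference. Only MORE brings people in for study sessions ("Participants randomized to the MORE condition will participate in eight, weekly, two-hour group sessions led by a clinic or study counselor"), and section 4.8 B pays a gift card for each. The direction cannot be predicted. The retention milestone counts MORE sessions, so it gives some protection to the MORE arm and none to TAU.

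If the pooled figure hid a badly followed arm, the larger trial could start with a follow-up method that fails in that arm, and its outcome comparison would be exposed to differential missing data. The placing of the both-groups phrase, beside the targets but not the benchmarks, also leaves room to argue about which reading was meant.

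**Working it through.** The plan does not convert its percentages into counts, so there is no figure of its own to reproduce beyond 15 + 16 = 31.

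**1. The bars.** The smallest count that meets proportion p among n people is p × n rounded up.

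| | Overall, n = 31 | MORE, n = 15 | TAU, n = 16 |
|---|---|---|---|
| 8 weeks, 65% | 20.15 → 21 | 9.75 → 10 | 10.4 → 11 |
| 16 weeks, 50% | 15.5 → 16 | 7.5 → 8 | 8 → 8 |

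The arm bars add up to the overall bars (10 + 11 = 21; 8 + 8 = 16). A per-arm rule therefore adds only a condition on how follow-up is split.

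**2. Splits that pass overall with one arm short.**

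- 8 weeks: 8/15 MORE (53%) + 13/16 TAU = 21; 12/15 MORE + 9/16 TAU (56%) = 21.
- 16 weeks: 4/15 MORE (27%, exact 95% CI 8–55%) + 12/16 TAU = 16; 12/15 MORE + 4/16 TAU (25%, 7–52%) = 16.

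The retention milestone does not rule these out: 8/15 attending at least four sessions is 53%, above its 50% bar. So the arithmetic of the concern is right.

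**3. How often the two readings disagree.** Take the arms as independent binomials, X ~ Bin(15, p_MORE) and Y ~ Bin(16, p_TAU). The pooled rule passes with probability P(X + Y ≥ 21) at 8 weeks and P(X + Y ≥ 16) at 16 weeks. The both-arms rule passes with P(X ≥ 10) × P(Y ≥ 11) and P(X ≥ 8) × P(Y ≥ 8). At the plan's own targets in both arms:

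| | Pooled | Both arms | Pooled pass, one arm short | of which short by one person |
|---|---|---|---|---|
| 8 weeks, 80% | 0.967 | 0.862 | 0.105 | 0.080 |
| 16 weeks, 75% | 0.999 | 0.975 | 0.023 | 0.018 |

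For both time points together (2,000,000 simulated trials, ranging from monotone dropout to independent time points), the pooled rule passes in 97% and the both-arms rule in 84–86%. An arm is short despite a pooled pass in 11–13%.

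If one arm is lower, at an assumed 70% and 60%, with the other at target, 85–88% pass overall and 26–34% pass with an arm short.

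**4. What those disagreements are.** In every scenario in step 3 the true rate in each arm is above the benchmark (80% or 70% against 65%; 75% or 60% against 50%). Each short arm is therefore sampling error in an arm that meets the standard. The 11–13% and 26–34% are false-alarm rates of a per-arm check, not rates at which the pooled rule hides a deficient arm.

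The striking splits in step 2 are rare. A pooled pass at 16 weeks with 4 or fewer followed in either arm has probability 0.009% at the targets, and 0.2–0.5% when one arm is at 60%.

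**5. A truly deficient arm.** This needs rates that the plan does not give. With MORE at an assumed 50% and TAU at 85% at 8 weeks, the pooled rule passes with probability 0.60 and the both-arms rule 0.15. With 35% and 75% at 16 weeks, the figures are 0.76 and 0.11. Here the rules do part company.

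**6. Precision at the arm bar.** Exact 95% intervals are 38–88% for 10/15 and 27–79% for 8/15. A pass or fail in a single arm says little about its true rate.

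**The case for a change.** The best case for a change is that the two readings can give different verdicts, that the choice should be fixed before data are seen, and that a sentence would do it. A per-arm check could leave the pooled gate untouched and ask only for a revised follow-up strategy where an arm falls short. Step 5 shows that, with a really poor arm, the pooled rule alone would often record success.

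Part of this stands. The pooled rule is blind to the split, and stating the basis and the denominator would be tidier. The denominator is also loose because section 4.2 A speaks of thirty participants. That is a clerical slip with no effect on the argument: with 30 the bars are 20 and 15, and at the 75% recruitment floor of 24 they are 16 and 12.

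The rest does not carry. The authors name both groups when they mean per arm and do not do so for the benchmarks, so the pooled reading is the natural one. A required response before progression would act as a second gate, triggered mostly by chance at this size.

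Nor does the pooled figure stand alone:

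- The 80% and 75% targets can be judged only by arm.
- Section 1.6 B makes completed and missed assessments a primary feasibility outcome.
- Section 6.1 A plans group comparisons, including dropout, although it sets no follow-up criterion by arm.
- Section 6.3 A has the DSMB review follow-up every three months.
- Section 1.10 requires a feasibility report and funder approval before the larger trial.

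An arm at 4/15 would be hard to miss.

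**Conclusion.** The concern does not call for a change. The benchmarks read as overall, 21/31 and 16/31, and that is a fair trade-off in a pilot whose arms are too small to judge singly. If follow-up runs at the plan's targets, a both-arms rule would fail about 11–13% of trials that pass overall, all by chance and mostly by one person. The protection that a per-arm rule would offer against a truly deficient arm is largely available from follow-up counts by arm, which the plan's own targets require.

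The missing word on the basis is a gap that analysts will fill sensibly by giving the overall rate among those randomised and the rate in each arm.

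This rests on a 15/16 split, independent arms and the 80% and 75% target rates. All other rates are assumptions used for illustration. It also rests on the milestones informing a judgement that the funder must approve; the plan states no automatic rule to proceed.
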